## B.3 Recruitment Procedures

Ads will be placed with several MSM-oriented “hookup” apps (e.g., Grindr, Scruff, Jack’d) to recruit participants into the study. Ads will display to users who login to the apps within 30 miles of each metro. Clicking on the ad will direct users to a landing page for the eTEST study, where users can learn about the study and its requirements. A brief questionnaire will assess eligibility criteria, and those eligible will then be directed to register for the study, which will involve providing informed consent, basic personal information, and baseline questionnaire data (see Human Subjects for more details about online informed consent). The web app will then randomize participants to one of the three arms. Finally, the web app will then walk participants through downloading the eTEST app from the Google Play or iTunes stores only if they were assigned to the enhanced eTest condition. Access to the eTEST app will be restricted to users registered in the eTEST web portal who are directed specifically from that site. Participants will also be encouraged to keep the app downloaded on their phone throughout the study period and will be encouraged to register any changes in their mailing address or smartphone information (number, phone OS) as soon as possible, either through the eTEST app, web portal, or by notifying study staff.

Once users have registered, staff will conduct a brief introductory call with all participants to ensure that their information is correct and that they understand the study’s requirements. After successfully completing this call, study staff will mark these participants as ‘fully enrolled,’ activating them in the study database.

#### **B.4 Design and Methods**

In the study phase, 2000 high-risk MSM who have not tested in the last year will be recruited from three metro areas, Providence/Boston, Jackson, MS, and Los Angeles, CA, using ads on MSM-oriented, geolocation-based mobile “hookup” apps. They will be randomized to receive one of the following at three month intervals over the course of a year: (1) HBST with remote monitoring and post-test phone counseling/referral (eTEST condition), (2) standard HBST without active follow-up, or (3) reminders to get tested for HIV at a local clinic, delivered via text messages (control condition). We chose a three month retesting interval (HBST/reminder) to align with the CDCs most stringent recommendations for high-risk MSM98. During the study period, participants will complete quarterly surveys online. At 12 months, participants will be asked to present to a local clinic to provide a blood sample for HIV testing, to facilitate exploratory analyses comparing the number of infections successfully detected in each group and the “time to diagnosis” in each condition (see 3C.3.5.2 for more detail).

#### **Experimental Conditions**

Only enhanced eTest participants will download the eTEST app. For these participants in the eTEST group, four HBST kits will be fit with BLE sensors and sent to participants. Follow-up calls will be made to these participants within 24 hours of opening their test to provide post-test counseling, referral for services, and a focused discussion on PrEP. In the standard HBST condition, four standard HBST kits will be sent at the same intervals, but will not be monitored and no follow-up calls will be provided. Standard participants will have a list of local resources (in Boston/Providence, L.A., or Jackson) depending on where participants are located included in the box with their test kit. This list of resources includes HIV/STD testing clinics, alcohol/drug and mental health treatment referrals, and the number for the national suicide prevention hotline,

as well as study staff contact information. These kits also, include a 24 hour helpline that participants can call with any questions or needs. In the control condition, participants will be reminded to get tested at a local clinic via text messages. Texts will link to the list of local clinics near them that conduct HIV testing, as well as their contact information/hours.

## **Measures**

After enrolling, participants will complete a baseline questionnaire assessing demographics, language barriers, immigration status, past HIV/STI testing history, recent use of other prevention/sexual health services, recent sexual behavior, alcohol/drug use, and mental health. These data will be useful for exploring barriers to testing, and changes in these variables over the study period.

### **Quarterly online questionnaires.**

Participants will also complete online questionnaires each quarter during the 12-month study period, which will be staggered and assigned one month after each testing interval to minimize possible conditioning effects. These surveys will assess HIV testing since the last study assessment, including whether they tested, how/where they tested, what their results were, whether each test was associated with PrEP care, or reasons for not testing. This approach will allow us to track contamination across conditions, or the extent to which those assigned to the control condition used a HBST or those in HBST conditions tested at a clinic. Questionnaires will also assess whether participants were referred for additional prevention services (e.g., STI testing, HIV risk reduction counseling), and whether they received these services since the last survey. Items will also assess whether participants consulted with a medical provider about PrEP in the last month, and if so, their provider's information and whether they were prescribed PrEP. Finally, as a compliment to passive app data, questionnaires will also assess app usage. These surveys will also assess constructs relevant to the behavioral, emotional, and social effects of HBST, including sexual risk behavior (online Timeline Follow Back), emotional health (PANAS-X), health empowerment, and social support. Finally, these surveys will also assess financial strain, insurance, housing instability, stigma, and medical mistrust, given evidence that these factors may be barriers to testing.

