## Planned Analyses

Analyses will be conducted in Year 5. To evaluate Aim 1(a), we will use factorial logistic regression to test whether rates of having completed any HIV test over the 12 month study period (assessed via self-report and/or clinic records) differ by study condition. Condition, study site (and their interaction) and other relevant covariates will be entered as predictors, allowing us to explore whether each condition's effects differ by study site. To explore the effects of study condition on regular HIV testing, we will use a generalized estimating equation (GEE) for repeated, binary outcomes, specifying whether participants tested during each 3-month study period as the focal outcome. A logit link function and independent correlation structure will be specified, with study condition, site, and relevant covariates as predictors, to test whether the odds of testing differ across time period, condition, and site. GEEs are a fitting approach for studies in which correlations between repeated measures variables are to be controlled, rather than a central focus of the analysis. For all models of **HIV testing** outcomes, a covariate reflecting whether a given participant had initiated PrEP (and when, for longitudinal models) will be added to each model, since these individuals are required to test for HIV quarterly as a part of ongoing PrEP care. Doing so will allow us to estimate the effects of study arm on HIV testing among those who did not initiate PrEP. Given that we have proposed collecting 54 more participants per site (162 total) than is required to estimate our most complex model (see Model 1b in Section 3C.3.10), we believe we will be fully powered to test this model, even with a high rate of PrEP adoption. While contamination of the control group in our pilot study was rare (only one control participant reported using a HBST), we will also track **where** each participant tested (at home, in person) in quarterly surveys. If contamination is significant, we will employ methods aimed at reducing this bias, including adding indicators of contamination as covariates or bootstrapping. To evaluate Aim 1(b), we will generate variables reflecting whether participants received testing for other STIs or risk reduction counseling during each of the four 3-month intervals of the study period. Similar GEE models will be estimated for these outcomes with time period, condition, and site as predictors, to test whether the odds of receiving each service differ across these factors. To evaluate Aim 2, we will code variables indicating whether participant reports or clinic records reflect participants having consulted with a medical provider about PrEP and/or received a PrEP prescription any time across the study period. Factorial logistic regression with study site, condition, and their interaction will be entered as predictors of this outcome, to test whether the odds of having received consultation and/or a PrEP prescription differ across each of the study sites and conditions. Overall, data from those who drop out or withdraw from the study will be used in these analyses, in intent-to-treat (ITT) fashion. Similarly, we will assume values of zero for all outcomes (i.e., non-receipt of testing or services) when quarterly assessments are missing but participants are retained in the study. Depending on the degree of missing assessments, we will use multiple imputation for these values, since data from missing assessments will likely be missing not at random.

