As in our pilot study, to avoid influencing the study results, participants in HBST conditions (eTEST and standard HBST) will not be given explicit instructions about whether or not to use the tests sent to them (except during eTEST follow-up calls, which will encourage re-testing every 3 months). They will be informed that HBST kits will be sent to them 1 week, 3 months, 6 months, and 9 months after initially signing up, and that they can choose to take these tests or not. For eTEST participants who choose to take the tests, they will be informed that they should expect a call from an HIV test counselor within 24 hours of opening it, and that these calls are intended to provide post-test counseling, information about HIV prevention, and referrals. Push notifications on participants’ smartphones will also notify participants at the time their test kits are opened that it was detected and that they should expect a call. Participants can

refuse any part of the discussions with counselors at any time. All participants will also be informed that, should they indicate having tested positive using an HBST through the quarterly surveys, a test counselor will follow up with them within 24 hours to ensure that they have made an appointment at a local clinic for confirmatory testing and care, if needed. If not, counselors will facilitate scheduling this appointment during their calls with these participants.

For eTEST participants that open their tests, counseling calls will be placed within 24 hours. These calls will be made by paraprofessional, Bachelor's level staff members who are employees of the Brown University School of Public Health, work in a "call center" physically located at Brown University, and who have been certified as 'Qualified HIV Test Counselors' in Rhode Island. This training ensures that candidates have basic knowledge of HIV and other sexually transmitted infections, understand HIV testing and how to conduct the test, and are familiar with counseling strategies needed to address many of the issues that commonly arise in those being tested. The training is conducted each year by [name] (Co-PI). Counselors will also receive training in triaging crisis intervention, which is provided by behavioral health staff at Lifespan. Clinical assessment and analysis of mental health will remain a responsibility of the licensed study clinician.

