**B.5.1.2. Online self-report questionnaires.** Online questionnaires will be used to collect self-report data as part of the baseline and quarterly follow-up assessments. These questionnaires will be developed and hosted using Qualtrics, which is a web application that affords custom development of web-based surveys. Qualtrics allows strict password protection and limited survey access which ensures that only essential research personnel at the study site will have access to the study data. For these reasons and others, Qualtrics can be used to collect many types of sensitive data, including 21 CFR Part 11, FISMA, and HIPAA data. Surveys can also be mobile-optimized within Qualtrics, allowing study participants to complete surveys on a variety of devices. Qualtrics is currently used by our research team.

**B.5.1.3. Audiotapes of post-test counseling phone calls.** Phone calls between test counselors and eTEST condition participants will occasionally be recorded for the purposes of conducting supervision with test counselors. These tapes will be collected using electronic recording equipment and will be stored in digital files on Brown University's servers. However, they will be stored only until the next supervision meeting (weekly) and will be deleted immediately afterward.

**B.5.1.4. Clinic records verifying service use.** We will also review the records of area clinics to compare with self-report data for each of the proposed outcomes (e.g., HIV testing, STI testing, PrEP consultation, receipt of a PrEP prescription). To facilitate this, participants will be asked to sign and return a HIPAA release in the case that they tested outside of the site clinics. The study informed consent process will also specifically ask participants to consent to allowing us to release limited personal information that reveals their participation in the study to the clinics they

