identify for the purposes of verifying service receipt and collecting limited clinical data (e.g., HIV/STI test results, and if positive, CD4 counts and viral loads). Quarterly online surveys will ask participants to name the specific clinics where they received each of the services that the questionnaires inquire about, and site-specific RAs will then request records from these clinics for these participants. Site-specific RAs will download participant data to explore service utilization and compile lists of participants who noted receiving services at each clinic. RAs will then contact each clinic that a participant utilized for HIV/STD testing. Once clinic data is received, site-specific RAs will code it using participants' unique study ID numbers and store it in password-protected files on Brown University's secure servers.

We realize that not all services will be verifiable (e.g., anonymous HIV testing), and that some participants may not be comfortable signing broad releases for their medical information. We also acknowledge that requiring the release of personal medical data may serve as a barrier to enrolling for some participants. At the same time, we also believe it is important to collect more objective data that can serve as a compliment to self-report whenever possible. Given these considerations, returning a signed release will not be required in order to enroll in the study, to prevent this procedure from acting as an impediment to enrollment. Instead, we will verify clinical service information for those who return their releases and consent to this specific procedure. This approach will allow us to verify as much clinical service data as possible, while minimizing participant discomfort with the study's procedures. While this likely means that data on clinical service use will be incomplete, we do not believe that incorporating this procedure undermines the importance of self-report data or the study as a whole. (See Section B4 for a full list of data collected from clinics.)

\*Data Use Agreements will be put in place to allow staff at each study site access to the study database (saved on Brown's servers) in order to verify service use and enter data collected.

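### The quarterly survey asks about PrEP consultation over the last month only, while the Aim 2 outcome counts consultation or prescription at any time in the 12 months

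*Combined protocol and SAP*

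**What the plan says.** **Survey item.** Under Quarterly online questionnaires: "Items will also assess whether participants consulted with a medical provider about PrEP in the last month". The provider's details and any prescription are asked only if the answer is yes.

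**Outcome.** Under Planned Analyses, Aim 2 is coded from participant reports or clinic records as "having consulted with a medical provider about PrEP and/or received a PrEP prescription any time across the study period".

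**Other items in the same survey.** HIV testing is asked about since the previous assessment. For other prevention services the survey asks "whether they received these services since the last survey". Each HIV test is also flagged for whether it was linked to PrEP care.

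**Timing.** Surveys are quarterly, "which will be staggered and assigned one month after each testing interval". Section B.5 says that "HBST kits will be sent to them 1 week, 3 months, 6 months, and 9 months after initially signing up", and that using them is optional.

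**Clinic records.** Section B.5.1.4 covers each proposed outcome, including PrEP consultation and prescription. Participants "name the specific clinics where they received each of the services that the questionnaires inquire about", and staff request records from those clinics. Participants are asked to "sign and return a HIPAA release in the case that they tested outside of the site clinics". Returning a release is not a condition of enrolment, and the section expects incomplete data.

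**eTEST calls.** Under Focused information/counseling on PrEP, eTEST participants who showed interest at an earlier call are asked later whether they made an appointment or initiated PrEP. No other arm receives these calls.

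**The concern.** An any-time outcome needs data sources that together span the whole period. Here the main all-arm source looks back one month in each quarter, and the prescription question inherits that limit. No reason is given for treating PrEP differently from HIV and STI testing.

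At stake are the absolute Aim 2 rates by arm, the PrEP care continuum promised by condition in Specific Aim 2, and the linkage rates that feed the cost-effectiveness model. Power for modest differences is also at stake. A second issue is comparability. If the eTEST call reports count as participant reports, one arm has a source of PrEP information that the other two lack, and the plan does not say whether they count.

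**Working it through.** The plan gives no figure that depends on the recall window, so there is none to reproduce. The check has three steps.

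**1. Calendar coverage.** Interventions fall at months 0, 3, 6 and 9 (Procedure). Surveys one month later fall at about months 1, 4, 7 and 10. A one-month look-back then observes months 0-1, 3-4, 6-7 and 9-10, which is 4 of 12 (33%). The payment text refers to five quarterly surveys, and the stated total agrees: 6 x $25 + $50 + $50 = $250. The date of the fifth is not given. At month 12 it would raise coverage to 5 of 12 (42%); at month 13 coverage of the study period stays at 4 of 12.

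**2. From months covered to events captured.** These fractions equal event capture only if events are spread evenly and nothing else recovers them. Because the windows follow each kit or reminder, prompted events may cluster inside them. For a consultation prompted by an eTEST call to be caught, delivery, opening, call and appointment must all fall within about a month, or about three weeks for the first kit, which goes out at week 1.

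As an illustration, assume an exponential lag from kit to consultation with parameter L weeks, truncated at 13 weeks, and a 4.33-week window:

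capture = (1 - exp(-4.33/L)) / (1 - exp(-13/L))

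| L (weeks, assumed) | Capture |
|---|---|
| 2 | 0.89 |
| 4 | 0.69 |
| 6 | 0.58 |
| 8 | 0.52 |

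The documents give no consultation timing, so these values only show the range.

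**3. Effect on rates and power.** Inputs:
- Pilot consultation, 25% eTEST v 4% control, and pilot PrEP starts, 10% v 4% (Significance). The second pair serves as a smaller illustrative contrast.
- N = 2000. Equal allocation is assumed: about 2000/3 = 666 per arm, and 666/3 = 222 per arm within one site.
- Alpha 0.05 (Power Considerations), taken as two-sided.

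Recorded rate = true rate x capture c, with c equal in both arms. With p the mean of the two recorded rates p1 and p2, d their difference and n per arm:

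power = Phi{ [d - 1.96 sqrt(2p(1-p)/n)] / sqrt([p1(1-p1) + p2(1-p2)]/n) }

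| c | 25% v 4% recorded as | Difference (points) | Odds ratio | Power, 222/arm | 10% v 4%: power, 666/arm |
|---|---|---|---|---|---|
| 1 | 25.0 v 4.0 | 21.0 | 8.0 | >0.999 | 0.991 |
| 0.89 | 22.3 v 3.6 | 18.7 | 7.8 | >0.999 | 0.981 |
| 0.52 | 13.0 v 2.1 | 10.9 | 7.0 | 0.993 | 0.861 |
| 0.417 | 10.4 v 1.7 | 8.8 | 6.9 | 0.974 | 0.774 |
| 0.333 | 8.3 v 1.3 | 7.0 | 6.7 | 0.933 | 0.677 |

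Worked line, 10% v 4% at c = 1/3: recorded 3.33% v 1.33%, d = 0.0200, p = 0.0233. The null standard error is 0.00827 and the alternative 0.00825. Then (0.0200 - 1.96 x 0.00827)/0.00825 = 0.46, and power = 0.68.

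With equal capture, the odds ratio and the test for a large contrast hold up well. The absolute rates and their difference shrink in proportion to c.

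**The case against.** The best defence is that the survey is not the only source. Section B.5.1.4 and Clinic records provide for PrEP consultation and prescription to be checked in records, and the survey collects the PrEP provider's details. A man who starts PrEP must test quarterly as part of that care. His tests are asked about since the last assessment, flagged if linked to PrEP care, and can lead to records with no one-month limit. One hit is enough for an any-time outcome. This stands: for men who start PrEP, 33-42% capture is near the worst case. It does not close the gap, because a PrEP provider is named through the same one-month item, and records depend on consent and an optional release. A single consultation outside the window that leads to no PrEP care can be missed by both sources.

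Four stronger readings are tempting but not supported.
- **That 58-67% of events are lost.** That is the share of months outside the windows. Clustering and record recovery make the event loss smaller by an unknown amount.
- **That PrEP providers' records are never sought.** The sentence "RAs will then contact each clinic that a participant utilized for HIV/STD testing" could be read this way, but the same section lists PrEP consultation and prescription among the outcomes to be verified and says records are requested from the clinics named.
- **That the bias favours eTEST.** Prompted consultations may cluster in the eTEST windows, but control participants are directed to clinics and may be likelier to name one whose records can be searched. Any assumed unequal capture gives a spurious effect of whatever size one chooses. The documents fix neither size nor direction.
- **That PrEP initiation is not collected.** The instruments are not shown, and Clinic records refers to self-reported PrEP uptake. The survey summary's silence does not prove the item is absent.

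**Conclusion.** The mismatch is plain in the text and should be fixed. Followed as written, the survey observes PrEP consultation and prescription in about 4 to 5 of 12 months for an outcome defined over all 12, and the other sources recover the remainder only in part. Aim 2 rates, the care continuum and the cost-effectiveness inputs will be too low by an unknown amount, mainly through one-off consultations.

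The main pilot contrast is not in danger. A contrast near 10% v 4% could lose material power, but the 68-77% figure assumes evenly spread events, equal capture in the arms and no help from records. Using eTEST call reports as outcome data would make ascertainment unequal between arms.

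Confidence is high on the mismatch and low on its size. A related gap is visible in the text: Specific Aim 2(b) names initiation, but Planned Analyses models only consultation and prescription for Aim 2.

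**What to change.** 1. In all arms, ask about PrEP consultation since the last survey and, as a separate question, about prescription over the same period, each with provider and date. State the date of the fifth survey. At month 12 or later, the windows would cover all 12 months.
2. State that Aim 2 outcomes are built from surveys and clinic records collected in the same way in every arm, and that eTEST call reports are used for process description only.
3. Check that the instruments collect PrEP initiation and its date, and add them if not. The HIV testing models also need them, since they adjust for whether and when PrEP was started. Analyse initiation as the Aim 2(b) outcome.

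The cost is a few survey-item edits and some analysis wording, with no extra visits or staff. The drawback is a recall period of about three months instead of one, which the plan already accepts for HIV and STI testing. The change belongs in the instrument, because events never recorded may not be recoverable at analysis.
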